**Table 1: Details of Study Treatments**

	Preparations to be Administered		
	Placebo	Test Product (New Drug)- 0.8 g/day dose group	Test Product (New Drug)- 1.2 g/day dose group
Investigational Name	Not applicable	IBD98-M	IBD98-M
Manufacturer	Holy Stone Healthcare	Holy Stone Healthcare	Holy Stone Healthcare
Total Daily Dose	Not applicable	Mesalamine 0.8 g; sodium hyaluronate 92 mg (total 4 capsules)	Mesalamine 1.2 g; sodium hyaluronate 138 mg (total 6 capsules)
Dosage	Not applicable	2 test product capsules and 1 placebo capsule, BID	3 test product capsules BID
Route	Oral	Oral	Oral
Formulation	Capsule	Capsule	Capsule
Capsule Strength	Not applicable	Mesalamine 200 mg; sodium hyaluronate 23 mg	Mesalamine 200 mg; sodium hyaluronate 23 mg

## **8.2 Dosage Schedule**

Patients will be randomized to 1 of 3 treatment groups: IBD98-M 0.8 g/day (mesalamine 0.8 g with hyaluronate 92 mg), IBD98-M 1.2 g/day (mesalamine 1.2 g with hyaluronate 138 mg), or placebo. Three blinded capsules of study medication (1 capsule from each of the 3 bottles in the medication kit) will be taken by each patient orally with water twice a day (See section 8.4). Patients will be instructed to swallow the study medication whole without breaking or chewing. Patients will be required to take the medication twice a day and will be encouraged to take their medication at the same times every day (in the morning and evening). All doses taken during the study must be recorded in the patient's diary.

## **8.3 Study Treatment Assignment**

Patients will be assigned treatment according to a 1:1:1 randomization schedule produced by inVentiv. The randomization code will not be available to the Bioanalytical Division of inVentiv until the clinical and analytical phases of the study have been completed.

#### 8.4 Blinding

Blinding of study treatments to the patient, site staff, and Sponsor will be maintained during the study using a double-dummy technique. Each patient will be dispensed with an IVRS-assigned kit, labeled with a unique kit ID at Visit 2, Week 0. Each kit will contain 3 bottles labeled with A, B, and C. Each patient should take **1 capsule from each bottle** twice a day. Each kit shall contain sufficient supply for 6 weeks.

The study will be double-blind. Subjects will receive 1 of 3 different treatment kits, identical in appearance, as outlined in table below.

Treatment Group	Bottle A	Bottle B	Bottle C
IBD98-M 0.8 g/day	200 mg IBD98-M	200 mg IBD98-M	Matching Placebo
IBD98-M 1.2 g/day	200 mg IBD98-M	200 mg IBD98-M	200 mg IBD98-M
Placebo	Matching Placebo	Matching Placebo	Matching Placebo

#### 8.5 Treatment Accountability and Compliance

It is the responsibility of the Sponsor to ensure that study medications provided for this study are manufactured under Good Manufacturing Practices and are suitable for human use. It is the responsibility of the Sponsor to ship a sufficient amount of dosage units to allow inVentiv to maintain an appropriate sampling for the study, and for drug retention, according to Food and Drug Administration (FDA) regulation (21 CFR 320.38, 320.63). Study medication will be stored by inVentiv as per applicable requirements.

The medications will be stored in a locked, environmentally controlled medication room with restricted access. Container(s) will bear a label containing at least the name of the study drug, lot and/or batch number, and manufacturing and/or expiry/retest date and a unique kit number. Individual patient doses will be

dispensed according to the kit number as assigned by IVRS, at Visit 3. All study drug received at the site will be inventoried and accounted for throughout the study and the result recorded in the drug accountability/retention record according to the appropriate inVentiv Standard Operating Procedure.

Compliance will be assessed by determining the amount of unused medication. Records will be kept of all medication dispensed, used, and returned by each patient. All doses taken during the study must be recorded in the patient's diary. The medication bottles (partial and empty) must be checked at the end of the study and compliance recorded on the Dosage Administration Record of the eCRF. At the end of the study, all unused trial medication and used packaging will be returned to the Sponsor. All study medication will be accounted for and any discrepancies documented.

## **8.6 Prior and Concomitant Illnesses, Procedures, and Medications**

### **8.6.1 Prior and Concomitant Illnesses**

Investigators should document all prior significant illnesses that the patient has experienced within 3 months prior to screening and in line with entry criteria. Additional illnesses present at the time when informed consent is given and up to the time of first dose are to be regarded as concomitant illnesses. Illnesses first occurring or detected during the study and/or worsening of a concomitant illness during the study are to be documented as adverse events (AEs) on the eCRF.

### **8.6.2 Concomitant Procedures**

All procedures that are performed during the study must be recorded in the patient's source documents and in the eCRF. The following should be taken into account with regard to concomitant procedures:

- Patients may not undergo major elective surgery while enrolled in this study.
- Patients may not donate blood, sperm, or oocytes during the study and for 6 months after the last dose of study drug.

### **8.6.3 Prior and Concomitant Medications**

Patients must follow the medication restrictions outlined in the inclusion and exclusion criteria (Sections 7.1 and 7.2) during the study. The use of hormonal contraceptives will be allowed and documented. Any concomitant medication use other than the occasional use of acetaminophen will be evaluated on a case-by-case basis by the Investigator. All concomitant medication use will be documented.

The use of the following medications is prohibited during the study:

- Rectal 5-ASA, budesonide, or steroids
- Systemic (oral or intravenous [IV]) corticosteroid
- Oral or parenteral immunosuppressants for treatment of UC
- Antibiotics for treatment of UC

## **9 STUDY PROCEDURES**

Table 2 outlines the timing of procedures and assessments to be performed throughout the study. See Sections 錯誤! 找不到參照來源。 to 11.8 for additional details of study procedures.

**Table 2: Schedule of Events**

STUDY PROCEDURE	Screening		Treatment Period				Follow-up Visit 7
	Visit 1 (Screening)	Visit 2 (Baseline)	Visit 3	Visit 4	Visit 5	Visit 6/Early termination	
DAY	--28 to -7	-14 to -1	0(± 1 day)	14(± 3 days)	28(± 3 days)	42(± 3 days)	56(± 3 days)
Informed consent	X						
Demographics / Medical History	X						
Confirm Study Eligibility	X	X	X				
Vital Signs	X	X	X	X	X	X	X
Physical Examination	X		X	X a	X a	X	X
Weight and Height	X					X	
12-Lead ECG	X					X	
Hepatitis Screening	X						
CBC with differential	X		X	X	X	X	X
Coagulation (aPTT, PT, INR)	X			X		X	
Serum Chemistry	X		X	X	X	X	X
Urinalysis	X		X	X	X	X	X
Pregnancy Test b	X		X		X	X	
Adverse Events	X	X	X	X	X	X	X
Concomitant Medications	X	X	X	X	X	X	X
UCDAI c		X	X	X	X	X	
IBDQ, SF-36			X			X	
CRP			X		X	X	
Flexible Sigmoidoscopy			X d			X	
Distribution of Diary / Check	X	X	X	X	X	X	
Stool for culture, C. difficile toxin, and ova & parasite	X						
Randomization			X e				
Treatment Distribution / accountability			X	X	X	X f	
Stool calprotectin			X			X	

Abbreviations: AE=adverse event; ECG= electrocardiogram; aPTT= activated partial prothrombin time; BMI= body mass index; PT= prothrombin time; INR= international normalization ratio; CRP=C-reactive protein; HRQoL= Health Related Quality of Life; IBDQ= Inflammatory Bowel Disease Questionnaire; C. difficile=Clostridium Difficile; eCRF=electronic case report form; UCDAI= Ulcerative Colitis Disease Activity Index

- a. Physical examinations performed on Days 14 and 28 should be abbreviated physical exams. New findings should be recorded as AEs
- b. Pregnancy test performed at screening should be serum test, after screening should be urine pregnancy tests
- c. UCDAI on Days 0 and 42 should be complete UCDAI score including the endoscopy subscore. UCDAI at Screening Visit 2, and Days 14 and 28 should be partial UCDAI score including only stool frequency, rectal bleeding and physician's global assessment
- d. Screening sigmoidoscopy must be performed on day -14 to -1
- e. To be performed prior to dosing
- f. On Day 42, there will be no study drug distribution

## **9.1 Patient Informed Consent**

Prior to performing any study-related procedures, the Investigator (or his/her designated staff member) will obtain written informed consent from the patient.

## **9.2 Procedures by Study Visit**

Assessments are to be performed as outlined in the following by-visit subsections.

### **9.2.1 Screening Period: Visit 1 (Days -28 to -7) and Visit 2 (Days -14 to -1, Baseline)**

The first screening visit will occur within -28 to -7 days prior to Day 0. The following procedures will be performed:

- Informed consent
- Demographics data collection: date of birth, country, gender, and ethnicity
- Physical examination (including weight and height for body mass index [BMI])
- All current and past medical conditions and disease history
- Verification of inclusion and exclusion criteria
- Vital signs (pulse, blood pressure, and body temperature) measurements
- 12-lead ECG
- Serology for HIV, and Hepatitis B and C
- Hematology assessments: complete blood count (CBC) with differential, activated partial prothrombin time (aPTT), prothrombin time (PT), and international normalization ratio (INR)
- Serum chemistry
- Urinalysis
- Serum sample for pregnancy test
- Recording of AEs and concomitant medications
- Stool sample for *C. difficile*, culture, and calprotectin
- Distribution of diary

The second screening (baseline) visit will occur within -14 to -1 days prior to Day 0.

The following procedures will be performed:

- Verification of inclusion and exclusion criteria

- Vital signs (pulse, blood pressure, and body temperature) measurements
- Recording of AEs and concomitant medications
- UCDAI
- Flexible sigmoidoscopy
- Distribution of diary

### **9.2.2 Treatment Period: Visit 3 (Day 0 [ $\pm$ 1 day]; Randomization)**

All patients will undergo the following procedures:

- Physical examination (including weight and height for BMI calculation)
- Vital signs (pulse, blood pressure, and body temperature) measurements
- Verification of inclusion and exclusion criteria
- Hematology assessments: Complete blood count (CBC) with differential
- Serum chemistry, including C-reactive protein (CRP)
- Urinalysis
- Urine pregnancy test
- Recording of AEs and concomitant medications
- Randomization via IVRS
- Check diary
- UCDAI
- Inflammatory Bowel Disease Questionnaire (IBDQ); 36-Item Short Form Questionnaire (SF-36)
- Stool sample for calprotectin
- Reserve blood sample
- Distribution and check of diary
- Blinded study medication distribution

### **9.2.3 Treatment Period: Visits 4, 5, and 6 or End-of-Study Visit, or Early Termination Visit (Days 14, 28, and 42) ( $\pm$ 3 days)**

All patients will undergo the following procedures:

- Physical examination (weight and height at Visit 6 only)
- Vital signs (pulse, blood pressure, and body temperature) measurements
- ECG (Visit 6 only)

- Hematology assessments: CBC with differential at Visits 4, 5, and 6; and aPTT, PT, and INR at Visit 4 only
- Serum chemistry (CRP at Visit 5 and 6 only)
- Urinalysis
- Urine pregnancy test (at Visit 5 and 6 only)
- Recording of AEs and concomitant medications
- UCDAI
- IBDQ; SF-36 (only at Visit 6)
- Check diary and distribution of diary (except Visit 6)
- Blinded study medication distribution (except at Visit 6)
- Stool sample for calprotectin (only at Visit 6)
- Reserve blood sample
- Flexible sigmoidoscopy (only at Visit 6)

#### **9.2.4 Follow-up Period: Visit 7 (Day 56 [ $\pm$ 3 days])**

Patients who prematurely withdraw from the study for any reason should complete the Early Termination Visit requirements. If the Early Termination Visit is not done, the reason(s) will be recorded in the CRF. All patients will undergo the following Visit 7 procedures:

- Vital signs (pulse, blood pressure, and body temperature) measurements
- Physical examination
- Hematology assessments: CBC with differential
- Serum chemistry
- Urinalysis
- Recording of AEs and concomitant medications

## 10 EFFICACY ASSESSMENTS

### 10.1 Ulcerative Colitis Disease Activity Index (UCDAI) Score

The modified UCDAI score will be used for assessment of efficacy during the study. Subjects are strongly encouraged to complete the symptom diary on a daily basis throughout the study.

#### Timing of diary entries for UCDAI

- At Baseline (Day 0), the timing of the diary entries depends on when the endoscopy is performed
  - If the endoscopy is performed within 5 days of randomization (Day 0), use the diary entries from 3 consecutive days immediately prior to the preparation day for the endoscopy.
  - If the endoscopy is performed 6 to 14 days prior to the randomization day (Day 0), the diary entries from 3 consecutive days immediately prior to Day 0 should be used.
  - The endoscopy must be performed within 14 days of randomization (Day 0).
- For visits where an endoscopy is not needed (Day 14 and 28), diary entries from the 3 days preceding the visit day will be used for the assessment of stool frequency, rectal bleeding, and physician's global assessment.
- For the Day 42 visit, diary entries from the 3 days preceding the visit day or the preparation for endoscopy, whichever comes first, will be used for the UCDAI assessment. Endoscopy must be performed within 3 days of the target visit day.

See Appendix 1 for further detail.

### Endoscopy subscore of the UCDAI

Sigmoidoscopy will be conducted during the second screening visit (for baseline UCDAI) and at Day 42 ± 3 days / early termination. The cleansing preparation should be conducted per site routine. The endoscopy performed at both visits should be a sigmoidoscopy, only the segment distal to the splenic flexure should be considered for purpose of endoscopy scoring (range from 0 to 3 points) per modified UCDAI (Appendix 1). Note that the modified UCDAI designates the presence of any friability as score of 2.

### **10.2 Inflammatory Bowel Disease Questionnaire (IBDQ)**

The Inflammatory Bowel Disease Questionnaire (IBDQ) will be used to measure disease specific quality of life (QoL). The IBDQ is a self-administered 32-item questionnaire that evaluates QoL across 4 dimensions: (1) Bowel – symptoms related to primary bowel disturbance, (2) Systemic symptoms, (3) Emotional function, and (4) Social function. The response to each question can range from 1 to 7, with 1 indicating severe problem and 7 normal health. The total IBDQ is computed as the sum of the responses to the individual IBDQ questions. The total score can range between 32 and 224, with higher scores indicating better QoL. IBDQ will be completed at Days 0 and 42. See Appendix 3.

### **10.3 Short Form-36**

The Short Form-36 (SF-36) questionnaire will be used to measure general health-related QoL. Individual subscale scores and two summary scores will be calculated: (1) physical component summary (PCS), which includes physical functioning, role-physical, bodily pain, and general health; (2) mental component summary (MCS), which includes vitality, social functioning, role-emotional, and mental health. SF-36 form will be completed at Days 0 and 42. See Appendix 4.

## 11 SAFETY ASSESSMENTS

Safety assessments (vital signs, physical examinations, periodic ECG recordings, AEs, SAEs, clinical laboratory results [routine hematology and biochemistry] are to be performed as specified in the Schedule of Events, Table 2.

### 11.1 Vital Signs

Vital signs (body temperature, respiration rate, heart rate, and blood pressure measurements) will be evaluated at the visits indicated in the Schedule of Events. All vital signs will be measured after the patient has been resting in a sitting position for at least 5 minutes. Blood pressure measurements are to be taken in the same arm for the duration of the study. Body weight (without shoes) will be recorded whenever vital signs are recorded, and height (without shoes) will be recorded at baseline only.

Vital sign measurements will be repeated if clinically significant or machine/equipment errors occur. Out-of-range blood pressure, respiratory rate, or heart rate measurements will be repeated at the Investigator's discretion. Any confirmed, clinically significant vital sign measurements must be recorded as AEs.

### 11.2 Physical Examination

A complete physical examination (heart, eyes, ears, nose, and throat [HEENT], heart, lungs, abdomen, skin, cervical and axillary lymph nodes, neurological, and musculoskeletal systems) will be performed at Screening Visit 1, Visit 3 and Visit 6. Physical examinations will be performed by a physician. In addition, medical history will be recorded at screening, including smoking history, if applicable.

A limited physical examination to verify continued patient eligibility and to follow any change in medical history will be performed at the visits indicated in the Schedule of Assessments (Visit 4 and 5). Symptom-driven limited physical examinations will be performed as clinically indicated at any study visit. All changes not present at

baseline or described in the past medical history and identified as clinically noteworthy must be recorded as AEs.

### **11.3 Electrocardiogram**

A 12-lead resting ECG will be obtained at the visits indicated in the Schedule of Events.

At screening, the Investigator will examine the ECG traces for signs of cardiac disease that could exclude the patient from the study. An assessment of normal or abnormal will be recorded, and if the ECG is considered abnormal, the abnormality will be documented on the eCRF. ECGs may be repeated if clinically significant abnormalities are observed or artifacts are present.

### **11.4 Laboratory Assessments**

Laboratory assessment samples (Table 3) are to be obtained at designated visits as detailed in the Schedule of Events.

**Table 3: Laboratory Assessments**

Blood Tests		
Hematology	Serum chemistry	Coagulation
Full and differential blood count Hematocrit (Hct) Hemoglobin (Hb) Mean corpuscular hemoglobin (MCH) Mean corpuscular hemoglobin concentration (MCHC) Mean corpuscular volume (MCV) Platelet count Red blood cell (RBC) count White blood cell (WBC) count with differential	Albumin Alanine aminotransferase (ALT) Alkaline phosphatase (ALP) Aspartate aminotransferase (AST) Blood urea nitrogen (BUN) or urea Creatinine Creatine phosphokinase (CPK) Electrolytes (Na, K,) Gamma-glutamyl transpeptidase (GGT) Glucose Lactate dehydrogenase (LDH) Total bilirubin Total cholesterol Triglyceride C-reactive protein (CRP)	Prothrombin time (PT) Activated partial thromboplastin time (PTT) INR (international normalization ratio)
Pregnancy test: A serum pregnancy test will be performed on all female patients of childbearing potential at the screening visit		
Urinalysis (dipstick)		
Appearance pH Protein Glucose Ketone bodies Indicators of blood and WBCs Specific gravity Urine human chorionic gonadotropin (HCG) (pre-menopausal females only) Urobilinogen		
Fecal calprotectin		

Blood and urine samples will be analyzed at a local laboratory facility. Urine samples will be analyzed by dipstick, and a microscopic analysis will be performed if the results of dipstick indicate abnormalities to be further investigated. Stool

samples will be collected and analyzed as described in Sections 11.5 and 11.6. All laboratory reports must be reviewed, signed, and dated by the Investigator. A legible copy of all reports must be filed with both the patient's eCRF and medical record (source document) for that visit. Any laboratory test result considered by the Investigator to be clinically significant should be considered an AE (clinically significant AEs include those that require an intervention). Clinically significant abnormal values occurring during the study will be followed until repeat test results return to normal, stabilize, or are no longer clinically significant.

### **11.5 Stool Sample for Cultures**

A stool sample will be obtained for culture, ova and parasite evaluation, and *C. difficile* assay. A sample will be collected and cultured during screening and at any point in the study when a patient becomes symptomatic, including worsening or return of disease activity.

### **11.6 Fecal Calprotectin Sample Collection**

A stool sample will be collected on Days 0 and 42 for the analysis of fecal calprotectin, a biomarker of intestinal inflammatory activity. Serum samples will be collected for CRP on Days 0, 28, and 42 for analysis of CRP, a blood biomarker for inflammation.

### **11.7 Diary Completion and Review**

During screening, patients will be instructed on how to appropriately complete the diary. The symptoms of UC must be recorded throughout the study, including the screening period. The patient diaries will be distributed at Visit 1 to record baseline data in the 7 days prior to Day 0. Diaries will be distributed at Visits 2, 3, 4, and 5 to

collect patient data during the treatment period. Diary entries will be reviewed by site personnel at the visits indicated in the Schedule of Events.

## **11.8 Adverse Events**

### **11.8.1 Adverse Events**

An AE is any symptom, physical sign, syndrome, or disease that either emerges during the study or, if present at screening, worsens during the study, regardless of the suspected cause of the event. All medical and psychiatric conditions (except those related to the indication under study) present at screening will be documented in the medical history eCRF. Changes in these conditions and new symptoms, physical signs, syndromes, or diseases should be noted on the AE eCRF during the rest of the study. Clinically significant laboratory abnormalities should also be recorded as AEs.

#### AE Reporting

Patients will be instructed to report AEs at each study visit. All AEs are to be followed until resolution or until a stable clinical endpoint is reached.

Each AE is to be documented on the CRF with reference to date of onset, duration, frequency, severity, relationship to study drug, action taken with study drug, treatment of event, and outcome. Furthermore, each AE is to be classified as being serious or non-serious. Changes in AEs and resolution dates are to be documented on the eCRF.

For the purposes of this study, the period of observation for collection of AEs extends from the time the patient gives informed consent until the follow-up visit (Visit 7). Follow-up of the AE, even after the date of therapy discontinuation, is required until the event resolves or stabilizes at a level acceptable to the Investigator.

Specific guidelines for classifying AEs by intensity and relationship to study drug are given in Table 4 and Table 5.

**Table 4: Classification of Adverse Events by Intensity**

MILD: An event that is easily tolerated by the patient, causing minimal discomfort and not interfering with everyday activities
MODERATE: An event that is sufficiently discomforting to interfere with normal everyday activities
SEVERE: An event that prevents normal everyday activities

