## APPENDIX 2 LABORATORY ABNORMALITY CRITERIA

Criteria for assessing marked abnormalities in safety laboratory parameters are based on Grade 2 moderate intensity levels from the Division of AIDS table for grading the severity of adult and pediatric adverse events (Version 1.0, December, 2004; Clarification August 2009).

Marked Abnormality Criteria for Safety Laboratory Parameters			
Parameter	Units	Direction of Change	Marked Abnormalities
HEMATOLOGY			
Hemoglobin	g/dL	Low Only	$\leq 7.0$ g/dL
Absolute Lymphocyte Count	$10^9$	Low Only	$<0.5 \times 10^9$
Leukocytes	$mm^3$	Low Only	Absolute Value $< 2,000/ mm^3$
Platelets	$mm^3$	Low Only	$<75,000/ mm^3$
Absolute Neutrophil Count	$mm^3$	Low Only	$<1000 mm^3$
Prothrombin Time	%	High Only	$>1.25 \times ULN$
CHEMISTRY			
SGPT	ULN	High Only	$>3.0 \times ULN$
SGOT	ULN	High Only	$>3.0 \times ULN$
Bilirubin	ULN	High Only	$>2.0 \times ULN$

---

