### 7.9.1 Adverse Events

All reported Adverse Event (AE) verbatim terms will be coded using the MedDRA dictionary version 17.0 or higher to provide the body system and preferred term.

A TEAE is defined as an adverse event that starts on or after the date of first dose of study medication. If the start date of an adverse event is incomplete or missing, the event will be assumed to be a TEAE, unless the incomplete start date (month and/or year) or the stop date (complete or incomplete) clearly indicates that the event started prior to dosing. Duration of the AE will be calculated in days as (AE stop date – AE start date) + 1, and will be calculated only for those events with both a complete start and stop date.

The relationship of each AE to study drug will be recorded as unrelated, unlikely, possibly, probably, and definitely. If a relation is missing for an AE, the relation of the event to study drug will conservatively be assumed to be definitely for summarization.

The severity of each AE will be classified as mild, moderate, or severe. If the severity of an AE is missing, the severity of the event will conservatively be assumed to be severe for summarization.

Number of events (e), number of patients (n) having an event, and percentage of safety patients (%) having an event will be presented by treatment group and overall for all AE and TEAE summary tables.

An overall summary of AEs and TEAEs will summarize the number of events, and the number and percentage of patients with events by treatment group and overall for the safety population.

The following categories will be included in this overall summary:

- at least one AE
- at least one related AE
- at least one SAE

- at least one related SAE
- at least one severe AE
- at least one TEAE
- at least one TEAE leading to discontinuation of study drug
- at least one related TEAE
- at least one related TEAE leading to discontinuation of study drug
- at least one serious TEAE
- at least one related serious TEAE
- at least one severe TEAE
- at least one related severe TEAE

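### Table 4 gives no size-based rule for grading silent laboratory AEs and is not reconciled with Appendix 2, so the severe-TEAE rows say little about silent laboratory toxicity

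*Protocol*

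**What the plan says.** Protocol Section 11.8.1 states: "Clinically significant laboratory abnormalities should also be recorded as AEs". The text after Table 3 in Section 11.4 agrees and leaves the decision to the investigator: "Any laboratory test result considered by the Investigator to be clinically significant should be considered an AE". Neither place requires symptoms.

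The AE Reporting text asks for a severity for each AE and names the tool: "Specific guidelines for classifying AEs by intensity and relationship to study drug are given in Table 4 and Table 5". The three levels of the intensity table, from the top down, are these:

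- The highest level, severe, is "An event that prevents normal everyday activities".
- One step below, the moderate level needs both discomfort and an effect on function: "An event that is sufficiently discomforting to interfere with normal everyday activities".
- The mild level covers what the patient tolerates well, with daily life undisturbed.

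Protocol Appendix 2 lists single thresholds for nine laboratory parameters and gives their origin: "Criteria for assessing marked abnormalities in safety laboratory parameters are based on Grade 2 moderate intensity levels". It names the source as a published table for grading the severity of adverse events.

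Protocol Section 5.2.2 makes the incidence and severity of TEAEs a safety endpoint. SAP 7.9.1 uses the same three levels. It plans summary rows such as "at least one severe TEAE", with rows for severe AEs and related severe TEAEs, and tables of TEAEs and serious TEAEs by maximum severity. An AE with missing severity is counted as severe.

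**The concern.** The intensity scale asks how the patient feels and functions. Many laboratory abnormalities are not felt. If they must be recorded as AEs and graded on this scale, the size of the abnormality has no bearing on the grade. A statement in the study report that no severe TEAE occurred could then follow from the scale and not from the drug.

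The protocol also holds a second scale that does look at size. Appendix 2 takes its thresholds from an AE-severity table and describes their level with the same word, intensity, that Table 4 has in its title. Nothing says how the two relate, and no planned analysis uses Appendix 2. At stake is the meaning of the severity part of a named safety endpoint in a trial that measures liver enzymes, creatinine and blood counts at repeated visits.

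**Working it through.** The plan states no figure on this point, so there is none to reproduce. The check follows one silent laboratory result through the text.

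1. **Is it an AE?** Take two patients without symptoms, one with ALT at 3.1 × ULN and one at 20 × ULN, both judged clinically significant. Under Sections 11.4 and 11.8.1 both are AEs. Section 11.4 also remarks that clinically significant AEs include those needing an intervention; that criterion does not appear in Table 4.

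2. **Must it be graded by Table 4?** AE Reporting says so for AEs in general. Neither document gives a separate rule for laboratory AEs. NCI CTCAE stands in the protocol's abbreviation list, but the supplied text never applies it.

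3. **Which grade results?** Severe fails, because no activity is prevented. Moderate fails, because there is no discomfort and no interference. Mild is the only level left. The answer is the same for 3.1 × and 20 × ULN, since no definition mentions size.

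4. **What does Appendix 2 say of the same values?** Its ALT criterion is above 3.0 × ULN. Both 3.1 and 20 exceed 3.0, so both are marked abnormalities at a level that the protocol calls moderate. Appendix 2 has one threshold per parameter, so it does not separate the two values either. Its parameters are hemoglobin, lymphocytes, leukocytes, platelets, neutrophils, prothrombin time, ALT, AST and bilirubin. There is no creatinine or other kidney row.

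5. **What reaches the SAP tables?** Graded by Table 4, each event adds 0 to the severe rows and enters the maximum-severity tables as mild. If the severity field is left blank, the same event adds 1 to the severe rows. With 17 patients per arm, one patient is 1/17 = 0.059, or 5.9 percentage points. That difference can arise from form completion alone.

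6. **Do other outputs show size?**

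| Output | What it shows |
|---|---|
| Descriptive statistics with minimum and maximum (SAP 6, 7.9.4) | Size of extremes, no patient counts |
| Shift tables (SAP 7.9.4) | Low, normal, high or missing: direction only |
| Laboratory data listings and listings of clinically significant abnormalities (SAP 7.9.4) | Individual patients, no summary by size |
| Counts outside the normal range (Protocol 12.5) | Any excess, whatever its size |
| TEAEs by preferred term (SAP 7.9.1) | That the event occurred |
| SAEs (Protocol 11.8.2) | Events judged medically important |

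Silent toxicity is therefore visible. No table counts patients by magnitude, and none uses the Appendix 2 thresholds.

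**The case against.** A function-based intensity scale is a legitimate design choice, and nothing in the documents requires AEs to be graded by magnitude. Laboratory safety also has its own endpoint in Section 5.2.2, under systemic tolerance. An ALT of 20 × ULN would show in the maximum and in the listings, and with 51 patients the listings can be read line by line. All of this stands. It confines the point to the severity endpoint, but it does not make the severe rows informative about silent events.

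Four stronger readings are tempting, and the documents do not support them.

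- A reader might infer that Table 4 contradicts Appendix 2. Appendix 2 flags laboratory values and does not say that it sets AE intensity, so a value can be marked while its AE is mild without any instruction being broken. The two scales are unreconciled, not contradictory.
- A reader might extend the mismatch to kidney toxicity. Appendix 2 has no kidney parameter. The limit of Table 4 applies to creatinine, but there is no second label for it to disagree with.
- A reader might conclude that every laboratory AE must be mild. Table 4 is offered as a guideline, an event with symptoms can grade higher, and a missing grade counts as severe. The mild definition itself speaks of tolerated discomfort, so an unfelt result may be better described as not addressed than as plainly mild. That too calls for a stated rule.
- A reader might conclude that the trial would hide silent toxicity. The outputs listed in the working show otherwise.

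There is also a question of versions. The SAP is based on Protocol Amendment 3 and cites a Section 7.4 that the supplied protocol lacks. SAP 7.9.1 does not name Table 4. That it reports the Table 4 grade is a reasonable inference from the shared three levels, not a stated fact.

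**Conclusion.** The point holds in a limited form. As written, a wholly asymptomatic laboratory AE that has been graded is mild whatever its size. The severe and related-severe TEAE rows and the maximum-severity tables therefore carry little information on silent laboratory toxicity. The protocol already refers to a size-based severity table, but neither Table 4 nor Section 11.4 nor the SAP makes use of it.

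The documents give no expected rate of such events, so the number affected cannot be estimated; each patient regraded shifts a row by 5.9 percentage points in an arm of 17. The conclusion assumes a literal reading of Table 4, and that the protocol version behind the SAP kept Table 4 and Appendix 2 unchanged. It concerns how severity is reported and nothing in patient management. It is worth correcting before unblinding because the correction is cheap and the endpoint is a named one.

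**What to change.** 1. In Table 4, state that AEs that are laboratory abnormalities are graded by the severity table cited in Appendix 2, whether or not symptoms are present. Set out the mapping from that table to mild, moderate and severe before unblinding. Appendix 2 reproduces only one threshold per parameter, so the remaining grades must be written in from the cited source. Say also what applies to a parameter for which that source gives no grade.

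2. In the SAP, add a count by arm of patients with any post-baseline value beyond the Appendix 2 thresholds, placed beside the severity tables of 7.9.1. This count will not cover kidney function.

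3. Where intensities are already recorded, keep the investigator's grade in the planned tables. Show the laboratory-based grade, taken from the worst value during the event, as a supplementary summary. Samples are tied to visits and analysed at local laboratories, so state how an event without a sample is handled and which reference limits apply.

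The cost is a short text change, one added table and a derivation from data already collected. Some laboratory AEs will appear as moderate or severe, and the report must explain two severity displays.
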